8.4 Statistical Analysis

Descriptive statistics (means, and SD for continuous data and frequency counts for categorical data) will be used to summarize baseline socio-demographic variables (age, race, ethnicity, gender, education etc.) and clinical variables (illness duration, illness severity, etc) for participants randomly assigned to WSE or placebo. The efficiency of randomization will be examined by comparing the baseline characteristics between the two treatment groups using independent t-tests or contingency statistics (chi-square or Fisher's test). If appropriate, variables that are significantly different between the two groups at baseline will be empirically identified as potential confounders and will be included as covariates in subsequent multivariate analyses. The consolidated standards of reporting clinical trials (CONSORT) will be utilized to describe the screening of eligible participants, random assignment to WSE or placebo, reasons for withdrawal, participants forming the efficacy population and those who complete the trial, etc (<http://www.consort-statement.org>).

8.5. Safety Analysis

Safety analyses of vital signs, laboratory measures, body weight etc. will be evaluated for the safety population, either as continuous or categorical variables (for instance – normal, abnormal etc). Further, the treatment-emergent adverse events will be grouped by organ-system and tabulated by treatment assignment, and rates between treatments will be compared using contingency statistics (chi-square or other Fishers Exact test) for categorical variables and T-tests for continuous variables.

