3.3 Recruitment Targets and Timelines

3.4 Schedule of Events

Approximate Visit Intervals	V1	V2	V3	V4	V5	V6	V7	V8
				2 wks	4 wks	6 wks	8 wks	10 wks
Informed Consent, Urine Drug Test, Pregnancy test, Psychiatric		X						
Diagnosis and History, Medical History								
Labs, EKG ¹		X						X
PANSS, CGI, PSS ²	X	X	X	X		X		X
MCCB		X				X		X
BP, Pulse, Temperature Weight, Height ³	X	X	X	X	X	X	X	X
Sensoril or Placebo		X	X	X	X	X	X	X
Treatment Emergent Adverse Events or Serious Adverse Events			X	X	X	X	X	X

Visit Comments, Pill Counts ⁴	X	X	X	X	X	X	X	X
--	---	---	---	---	---	---	---	---

Visit 1 can be split up (if needed) into 2 visits for screening and spread over 1 to 4 weeks. Visit 2 is the randomization visit. Following randomization, visit intervals for V3 through V8 can range from \pm 4 days of the expected between interval visits; exceptions on a case by case basis by the study team.

Visits 1 and 8 will last roughly 2 hours. Visits 2, 3, 4, 5, 6, and 7 will last roughly 1 hour.

At Visit 1 – Urine drug test for illicit substances will occur as will a serum pregnancy test for women in the reproductive age group.

¹Labs: CBC + Diff, Chemistry 14? (including liver and renal functions, electrolytes, blood sugar, and lipid profile), urine analysis, and hs CRP and serum for cytokine panels

¹EKG: standard EKG

² The Positive and Negative Syndrome Scale (PANSS), Clinical Global Impression Scale (CGI), Perceived Stress Scale (PSS),

³ Height at screening only, waist circumference and BMI at screening and visit 8 or end of study.

⁴ Pill Counts – will start at visit 3, i.e., post randomization

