7.2. Study Treatments, Assessments and Follow up

After all screening procedures have been completed and reviewed and the participant remains eligible for the study, the participant will receive either Sensoril® or placebo at visit 2. The

participant will get one of these medicines by chance (like flipping a coin), and have a 1 in 2 chance of getting either Sensoril® or placebo. The medicine is packaged identically so that it is not possible to tell which is Sensoril® or which is placebo. The medicine will be given to the participant as capsules, and is taken by mouth. Starting at 1 capsule twice daily, the medicine (or placebo) will be increased to 2 capsules twice daily a week later, unless the participant is experiencing side effects. Neither the participant, or the doctor or the research staff will know if the participant is receiving Sensoril® or placebo.

If any tolerability issues emerge, further titration of study medicines can be stopped at a minimum 500 mg/day. If dosage has been increased to 1000 mg/day it can be decreased to 500 mg/day for side-effects.

Details of procedures at each visit (Visit 1 to 8) are described in the schedule of events (**3.2.c.**). Psychopathology ratings (details of the scales were described in **Section 3.2.d** earlier) are briefly mentioned in section 7.1.a. Safety assessments will include determination of side effects at each visit, and depending on the side effects, further clinical action will be undertaken. Laboratory measures at baseline and end point will provide more safety data as will careful monitoring of physical and psychological status at each visit.

If the participant would like to know the treatment assignment at the end of the data analyses and if a contact address or phone number is left with research staff, we will attempt to notify them of their treatment assignment during the study.

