8.1 Primary Endpoint(s)

For *Specific Aim 1*, an intention-to-treat strategy will be used for analysis and participants will be analyzed as part of the group to which they were randomized. A linear mixed model will be used to examine changes in measures of psychopathology (PANSS Total, Positive and Negative Symptoms and General Psychopathology Subscales) and psychosocial stress (PSS). For the primary endpoint (PANSS Total Score), a model that includes visit, treatment, visit * treatment interaction as fixed effects with baseline PANSS total score as a covariate will be used. Model-estimated marginal means for scheduled

visits will be computed per treatment group to examine time to response. Linear mixed models use all available data, account for non-independence of repeated measures and provide unbiased estimates if missing data are present.

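### Section 8.5 names only t-tests for continuous safety measures, with no baseline adjustment and no stated response; adjusting for the baselines already collected is a free gain in precision

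*Combined protocol and SAP*

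**What the plan says.** Section 8.5 opens with the measures at issue: "Safety analyses of vital signs, laboratory measures, body weight etc. will be evaluated for the safety population", and they may be handled "either as continuous or categorical variables". That sentence names no test. The next one turns to adverse events ("the treatment-emergent adverse events will be grouped by organ-system and tabulated by treatment assignment, and rates between treatments will be compared using contingency statistics") and ends by assigning contingency tests to categorical data and t-tests to continuous data: "for categorical variables and T-tests for continuous variables". Nothing in 8.5 states the response (end value or change), the visit compared, or a baseline covariate.

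The baselines exist. Section 7.2 states "Laboratory measures at baseline and end point will provide more safety data", and the row "BP, Pulse, Temperature Weight, Height" in the section 3.4 schedule is marked at every visit from V1 to V8 (height at screening only, by its footnote).

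Elsewhere the plan does use baselines. The primary efficacy model in 8.1 is fitted "with baseline PANSS total score as a covariate". Section 8.4 allows extra covariates, where appropriate, under a significance rule: "variables that are significantly different between the two groups at baseline will be empirically identified as potential confounders", for use in later multivariate analyses.

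**The concern.** Each of these safety measures has a baseline value, and the plan already adjusts its primary outcome for baseline. An unadjusted comparison of end values would carry all the between-person spread into the safety estimate. It would also carry in any chance difference between arms at baseline, which could then look like a drug effect or hide one. The trial is sized for efficacy only (8.6), with 33 per arm, so avoidable imprecision in safety matters. Because the response is not fixed, the choice between end value and change could also be made after the data are seen.

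**Working it through.** **Inputs.** From the documents: 33 per arm (8.6) and 1:1 allocation (3.2). Chosen for illustration: two-sided 5% and 80% power. Assumed: equal SDs at baseline and end and in both arms, and r between 0.3 and 0.95. The one degree of freedom spent on the covariate is ignored.

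**The plan's own figure.** The documents give no power or precision figure for safety. The efficacy calculation in 8.6 reproduces: a two-sample t-test with effect size 0.83 and 33 per arm has power 0.955 one-tailed and 0.913 two-tailed (stated: 0.95 and 0.90), and all eight entries of the sample-size table agree. It is not in dispute; only the 33 per arm is carried over.

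**Variance of the treatment difference**, relative to a t-test on end values:
- end-value t-test: 1
- change-score t-test: 2(1 − r)
- ANCOVA: 1 − r²

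**Share of precision lost against ANCOVA** = 1 − (ANCOVA variance / t-test variance):
- end value: 1 − (1 − r²) = r²
- change: 1 − (1 − r²)/[2(1 − r)] = 1 − (1 + r)/2 = (1 − r)/2

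The last column is the smallest difference detectable with 80% power, in SDs of the raw measure. The end-value t-test needs 0.70; the others multiply 0.70 by the square root of their relative variance.

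| r | Loss, end-value t | Loss, change t | Detectable: end / change / ANCOVA |
|---|---|---|---|
| 0.3 | 9% | 35% | 0.70 / 0.83 / 0.67 |
| 0.5 | 25% | 25% | 0.70 / 0.70 / 0.61 |
| 0.7 | 49% | 15% | 0.70 / 0.54 / 0.50 |
| 0.8 | 64% | 10% | 0.70 / 0.44 / 0.42 |
| 0.9 | 81% | 5% | 0.70 / 0.31 / 0.31 |
| 0.95 | 90% | 2.5% | 0.70 / 0.22 / 0.22 |

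For a true difference of 0.5 SD, power (end / change / ANCOVA) is 0.52 / 0.52 / 0.64 at r = 0.5, 0.52 / 0.73 / 0.80 at r = 0.7, and 0.52 / 0.99 / 1.00 at r = 0.9. At r = 0.5 either t-test makes 33 per arm perform like 33 × 0.75, about 25.

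**Body weight as an example** (SD and r assumed). Detectable difference = 2.8 × SD × √(2/33) for end values, times √(2(1 − r)) for change or √(1 − r²) for ANCOVA. The normal multiplier 2.8 gives 0.69 SD, against 0.70 from the exact t calculation.
- SD 15 kg, r = 0.98: 10.3 kg (end), 2.07 kg (change), 2.06 kg (ANCOVA)
- SD 20 kg, r = 0.95: 13.8 kg (end), 4.36 kg (change), 4.31 kg (ANCOVA)

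**Does the 8.4 rule cover this?** With 33 per arm, a baseline difference below about 2.0 × √(2/33) = 0.49 SD is not significant, so it triggers no adjustment. At an assumed SD of 15 to 20 kg that is about 7 to 10 kg. With no drug effect, an imbalance D is expected to reappear as rD in end values and as −(1 − r)D in change scores: 95% and 5% of D, respectively, at r = 0.95.

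**The case against.** A reader might infer that the trial gives up most of its precision to detect harm, or that a real shift in weight, liver enzymes or blood pressure would be missed. The documents do not support either. A loss above one half needs a t-test on raw end values and r² > 0.5, that is r above about 0.71, and the documents state neither. On change scores the loss cannot exceed 50% for r ≥ 0, and it is smallest where r is high. Setting 10 to 14 kg for weight against 2 to 4 kg with ANCOVA leaves out the change-score test, which nearly equals ANCOVA. Whether a given shift is missed depends on its size, on r and on the response. This objection stands in full and limits the claim.

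The t-test wording also sits in the adverse-event sentence, so its reach to weight, vital signs and laboratory values is inferred. That is fair. But it is the only test 8.5 offers for continuous data; on the narrower reading these measures would have no named comparison, and 8.5 would still need amending.

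Section 8.4 leaves a route to covariates. It depends on a significant baseline difference and refers to multivariate analyses, so it does not prespecify each measure's own baseline.

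Finally, the t-test is not the only means of detecting harm. Section 7.7 classes certain abnormal findings as adverse events, 8.5 compares adverse-event rates and allows normal/abnormal categories, and the DSMB has an incidence trigger in 7.4. This lowers the stakes but gives no reason to discard the baseline in the continuous comparisons.

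**Conclusion.** The point holds as a free improvement. Section 8.5 leaves the response undefined and does not prespecify adjustment for baselines the trial already collects. ANCOVA is at least as precise as either t-test at every r ≥ 0, apart from one degree of freedom. The size runs from trivial (2.5% of precision, change scores at r = 0.95) to about 90% (end values at r = 0.95); at r = 0.5 it is 25% with either t-test. For very stable measures the practical matter is to exclude an unadjusted end-value comparison; for measures with moderate r, ANCOVA improves on both t-tests. These sizes rest on assumed correlations and equal SDs, and on reading the t-test clause as covering vital signs, weight and laboratory values. No efficacy conclusion is affected.

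**What to change.** In 8.5 keep the contingency tests for categorical data and replace the t-test provision with:

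> Continuous safety measures will be compared at the final visit by ANCOVA (or the 8.1 mixed model where measured repeatedly) with treatment as the effect and the measure's own baseline value as a covariate, with log transformation for skewed laboratory values; estimates are reported with 95% CIs.

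The mixed model suits vital signs and weight, which the schedule records at every visit; ANCOVA suits laboratory values taken at baseline and endpoint. This also settles the response and the visit in advance. The cost is one sentence of analysis wording and one degree of freedom per model, with no new data or visits.

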8.6 Sample size calculation

In a previous 12-week, double-blind, placebo-controlled study that examined the efficacy of WSE (Sensoril®) for the treatment of symptom exacerbations in participants with schizophrenia (Chengappa et al, in press: J Clin Psychiatry), participants randomized to Sensoril® had a significantly greater reduction in PANSSS total score (effect size=0.83); the primary outcome measure in the current study. If we assume the same effect size, then a sample of 66 (33 in each group) will have a power of 0.95 to detect an effect size of 0.83 with a 1-tailed alpha set at 0.05 and power of 0.90 with a 2-tailed test of significance (see Table). The proposed sample size will allow for us to continue to have sufficient power (i.e., 0.80), even if a significant number of randomized participants fail to provide data for the proposed analyses.

Power	Sample (1-tailed)	Sample (2-tailed)
0.80	$19 + 19 = 38$	$24 + 24 = 48$
0.85	$22 + 22 = 44$	$28 + 28 = 56$
0.90	$26 + 26 = 52$	$32 + 32 = 64$

0.95	33 + 33 = 66	39 + 39 = 78
------	--------------	--------------

9. Quality Control and Quality Assurance

Independent monitoring of the clinical study for protocol and GCP compliance will be conducted periodically by qualified staff of the UCLA and University of Maryland Human Subject Protection Offices.

The investigator-sponsor and the University of Maryland and UCLA will permit direct access of the study monitors and appropriate regulatory authorities to the study data and to the corresponding source data and documents to verify the accuracy of this data.

Details of the Data and Safety Monitoring Committee are noted in section **7.4**.

All individuals (P.I. and research staff) involved with the study will attempt to meet weekly throughout the duration of the research study to discuss and monitor confidentiality, data, recruitment and adverse events, including clinical outcomes relating to the participants in the study. At the weekly research meetings, the P.I. and all study personnel will be apprised of new developments relating to the study participants. Any unanticipated problems and unanticipated, serious adverse events felt to be possibly related or related to the research interventions will be reported to the University of Maryland and UCLA IRB's in accordance with the IRB's reporting requirements. Adverse events and reports from the data and safety monitoring will be reported to the IRB sooner if it changes the risk to benefit ratio of the protocol. In accordance with IRB adverse event reporting these will be in addition to the yearly summaries. A summary of all the unanticipated adverse events observed during the course of the study in a twelve-month period will be reported to the IRB at the time of the annual review.

All research data is recorded on Case Report Forms that will be stored in a locked file cabinet in study personnel's office. The research forms will not include any form of identifying information. ID numbers rather than subject identifiers are used to record information on computer databases which are protected by firewalls and only authorized personnel with user id and passwords are permitted to enter and view the data.

10. Data Handling and Record-Keeping

10.1. Data recording/Case Report Forms A Case Report Form will be completed for each subject enrolled into the clinical study. The investigator-sponsor will review, approve and sign/date each completed CRF; the investigator-sponsor's signature serving as attestation of the investigator-sponsor's responsibility for ensuring that all clinical and laboratory data entered on the CRF are complete, accurate and authentic. We will make all efforts to collect all data points associated with this research. Research staff will utilize various sources, including electronic medical record information for verification purposes, when available.

Source Data are the clinical findings and observations, laboratory and test data, and other information contained in *Source Documents*. *Source Documents* are the original records (and certified copies of original records); including, but not limited to, hospital medical records, physician or office charts, physician or nursing notes, subject diaries or evaluation checklists, pharmacy dispensing records, recorded data from automated instruments, x-rays, etc. When applicable, information recorded on the CRF shall match the *Source Data* recorded on the *Source Documents*.

Source Data

The data obtained from hospital record or laboratory or EKG reports or other relevant medical information done prior to or during the study will be considered source documents and kept in a file for each participant subject. Some of these data points – for example – laboratory reports and results, or vital signs, or body weight measurements will be recorded in the CRF binders, and in such instances these data will be source documents for participating subjects.

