3.1 Study Overview This proposal is a 12-week, double-blind, randomized, placebo controlled study of a standardized extract of WSE (target dosage: 1000 mg/day) added to ongoing antipsychotic treatment in mild to moderately symptomatic patients with either schizophrenia or schizoaffective disorder.

Treatment will begin on day 1 at 250 mg oral route, BID. (500 mg/day WSE or placebo) and titrated to 500 mg, po; BID (1000 mg/day) in week 2, for the rest of the study, unless tolerability issues dictate a lower dosage. Psychopathology and adverse events will be assessed at every visit. High sensitivity C-reactive protein (hs-CRP) and other inflammatory markers will be measured at baseline and end of the study.

3.2 Timelines, Visits, Assessments, Rating Scales, Study Medications, Laboratory and EKG and Adherence

After obtaining written informed consent, patients will be screened for eligibility and those who meet all the inclusion and exclusionary study criteria will be randomly assigned (in a 1:1 allocation ratio) to receive double-blind adjunctive treatment either with WSE or placebo for 12 weeks (Visits 2 through 8) see table below describing Schedule of Events. Participants will be seen at scheduled visits unless they

need to be seen sooner. The screening and consenting visits and visit 8 will last nearly 2 hours; the other visits will last about 60 minutes.

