3.5 Outcome Instruments

Psychopathology will be assessed using the Positive and Negative Syndrome Scale that measures the severity of psychotic and non-specific symptoms and is commonly used in

schizophrenia clinical trials, and a global assessment of the severity of illness (CGI) as well as change, i.e. improvement or worsening. The Perceived Stress Scale (PSS) will also be utilized.

Positive and Negative Syndrome Scale (PANSS): (Kay, Fiszbein et al. 1987) The PANSS is a psychiatric scale used for measuring symptom severity of patients with schizophrenia. It is widely used in clinical trials in schizophrenia. The scale measures the two main types of symptoms in schizophrenia; positive symptoms, which refer to an excess or distortion of normal functions (e.g., hallucinations and delusions), and negative symptoms, which represent a diminution or loss of normal functions (e.g. speech, activity, motivation, etc.). The PANSS is a relatively brief interview, requiring 20-30 minutes to administer. The interviewer will be trained to a standardized level of reliability.

Clinical Global Impression Scale: (Guy 1976) The Clinical Global Impression Scale (CGI) for Severity and Change subscales is an assessment of the clinical impression of the severity of illness and the change in severity of symptoms. A severity score of 1 indicates subject is normal, not ill, 2 indicates borderline mentally ill, 3 indicates mildly ill, 4 indicates moderately ill, 5 indicates markedly ill, 6 subject indicates is severely ill and 7 indicates the subject is among the most extremely ill. Improvement or worsening or no change is noted in the change subscale. The CGI is widely used in clinical trials in psychiatry.

Perceived Stress Scale (Cohen, Kamarck et al. 2000) The Perceived Stress Scale (PSS) was developed to measure of the degree to which situations in one's life are appraised as stressful. Psychological stress has been defined as the extent to which persons perceive (appraise) that their demands exceed their ability to cope. The PSS has become one of the most widely used

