5.2 Breaking the Blind

Blinding will be maintained by the dispensing pharmacists at the UCLA and MPRC research pharmacies and so the clinician team and study participants will remain blind to treatment assignment throughout the tenure of the study.

If unintentionally or intentionally (see next paragraph) the blind is “broken,” data collection will be stopped at that point for that individual participant. A case by case basis for completion of study procedures (i.e., even if efficacy data collection is stopped, safety data collection will

continue), if the participant would prefer to complete the study and the investigative team sees no reason that may harm the participant or the study goals, study completion may be permissible based on discussion with the Data and Safety Monitoring Board (DSMB).

If unblinding is absolutely necessary, the study PI will contact the research pharmacist to obtain the treatment assignment information and notify the appropriate entities as soon as feasible. (e.g. DSMB, IRB)

After completion of the entire study and after the data bases are “locked” and statistical analyses have been completed, if participants would like to know their treatment assignment, the research team will provide them that information.

Statistical analyses of primary and secondary outcomes will be carried out “blind” to treatment assignment. The treatment assignment to Sensoril® or placebo will be revealed upon completion of the main statistical analyses.

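### Section 9 shares participants' adverse events and clinical outcomes with all study personnel weekly and does not exempt the PANSS interviewer, which leaves an avoidable route to rater bias in the primary outcome

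*Combined protocol and SAP*

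**What the plan says.** Section 9 describes a standing team meeting: "All individuals (P.I. and research staff) involved with the study will attempt to meet weekly throughout the duration of the research study". Its purpose is to "discuss and monitor confidentiality, data, recruitment and adverse events, including clinical outcomes relating to the participants in the study". It adds that at these meetings "the P.I. and all study personnel will be apprised of new developments relating to the study participants". No member of staff is excepted.

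The primary endpoint is rated by an interviewer. Section 8.1 specifies: "For the primary endpoint (PANSS Total Score), a model that includes visit, treatment, visit * treatment interaction as fixed effects". Section 3.5 describes the PANSS as a 20-30 minute interview, and the only safeguard it states for the rater is training: "The interviewer will be trained to a standardized level of reliability".

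The blinding measures are these:

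- Section 5.2: the dispensing pharmacists keep the blind, "so the clinician team and study participants will remain blind to treatment assignment throughout the tenure of the study". If the blind is broken, efficacy data collection stops for that participant. The main analyses are done blind.
- Section 6.1: active and placebo capsules look alike and the smell is masked.
- Section 7.2: research staff, as well as the doctor and the participant, do not know the assignment.

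Section 3.1 says of the visits themselves: "Psychopathology and adverse events will be assessed at every visit". Section 7.3 has side effects elicited at each visit by an open question and a checklist. It does not say whether the person who does this also rates the PANSS.

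**The concern.** A PANSS score is a judgement. A rater who has heard in a meeting that a participant has had side effects, or has had capsules reduced because of them, may form a view about the arm and score the next interview accordingly. The allocation code need not be opened for this to happen.

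The resulting error would sit in the outcome data. Randomisation balances participants, not the rater's expectations. The mixed model in section 8.1 takes the scores as given, and analysing them blind does not correct scores that were already shifted. What is at stake is the validity of the primary comparison.

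**Working it through.** The point is procedural, so the main check is a reading of the passages together. The arithmetic only shows how sensitive the trial would be to a bias of a given size.

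**1. Does the rater fall within the meeting rule?** Section 9 defines the attendees as the P.I. and research staff and extends the information to all study personnel. A PANSS interviewer is study personnel on any ordinary reading, and the protocol describes no external or independent rater. Attendance is therefore inferred from the word *all*; raters are not named. The text also says only that staff will attempt to meet.

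**2. What would the rater hear?** Adverse events and clinical outcomes are on the stated agenda. Dose changes are not listed, but section 5.0 allows dose reduction for side effects, and such a change would naturally count as a new development. Section 8.2 also has the coding of psychotropic medication adjustments made simultaneously determined in research meetings.

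**3. Does any blinding measure close this route?** Pharmacy-held codes protect the list. Look-alike, odour-masked capsules prevent recognition of the product. The stopping rule in section 5.2 applies once the blind is broken, and an unspoken guess would not obviously trigger it. No passage keeps adverse-event information from raters, separates rating from side-effect assessment, or checks whether the blind held.

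**4. The plan's own figures.** Section 8.6 gives, for 33 per group, effect size 0.83 and alpha 0.05, power of 0.95 one-tailed and 0.90 two-tailed. With the noncentral t, df = 2 × 33 − 2 = 64 and noncentrality = 0.83 × √(33/2) = 3.37. Power is 0.955 one-tailed and 0.913 two-tailed. The stated figures reproduce, so the same model is used below.

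**5. Illustration of a rating bias.** The documents give no PANSS SD, guess rate or scoring shift, so all three are assumed. Suppose raters guess the arm correctly with probability g and score participants they believe to be on the extract s points better than those they believe to be on placebo. A fraction g of the extract arm and 1 − g of the placebo arm is then scored favourably, so

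bias = s × [g − (1 − g)] = s × (2g − 1).

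| | s (points) | g | Bias (points) | SD | Bias in SD units |
|---|---|---|---|---|---|
| Low | 3 | 0.65 | 3 × 0.30 = 0.9 | 18 | 0.9/18 = 0.05 |
| High | 4 | 0.80 | 4 × 0.60 = 2.4 | 12 | 2.4/12 = 0.20 |

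With no true effect, noncentrality = bias in SD units × √(33/2), on 64 df:

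| Bias (SD) | Noncentrality | Type I error, two-sided | Type I error, one-sided |
|---|---|---|---|
| 0 | 0 | 0.050 | 0.050 |
| 0.05 | 0.20 | 0.055 | 0.074 |
| 0.10 | 0.41 | 0.069 | 0.107 |
| 0.20 | 0.81 | 0.126 | 0.200 |

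The one-sided column is shown because section 8.6 quotes power for both kinds of test. It applies to a bias in favour of the extract.

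**6. What the illustration does not show.** It gives the effect of rater guessing from any source. Adverse events and psychopathology are assessed at the same visits, so a rater could learn of side effects without a meeting. The meeting's own increment cannot be calculated from the documents.

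**The case against.** The strongest reply is that section 9 leaves a procedural detail unstated and shows no flaw. Raters are not named as attendees, the meeting is only attempted, and the protocol has several layers of blinding, including one for research staff. The documents give no adverse-event rates by arm, so nothing shows that side effects would reveal allocation. Because ratings and side effects share visits, the meeting may add little. At the low end of the illustration, two-sided type I error of 0.055 is hardly distinguishable from 0.05.

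Much of this stands, and it limits the point to a possible bias of unknown size. It does not remove the point. Section 9 is a positive instruction to inform all study personnel, and the other blinding measures do not address inference from clinical information.

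A reader might go further in three ways that the documents do not support:

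- **Pharmacists at the meeting.** One might infer that the pharmacists who hold the codes attend as well. Section 9 itself glosses the attendees as the P.I. and research staff. Section 5.2 makes the pharmacists keepers of the blind, and section 7.2 says research staff do not know the assignment. Nothing suggests that code-holders discuss assignments with the team.
- **Earlier scores.** One might want raters kept from all earlier ratings. The CGI Change subscale in section 3.5 records improvement or worsening and so needs the earlier state as a reference. Knowing earlier scores without guessing the arm is also not shown to favour either arm.
- **Bias as a fact.** One might conclude that side-effect guesses will shift the arms' scores apart. That requires side effects or dose changes that differ by arm, which the documents do not establish.

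**Conclusion.** The point holds in a limited form. As written, section 9 gives all study personnel participants' adverse events and clinical outcomes and does not exempt the PANSS interviewer. If side effects or dose changes differ by arm, this is an avoidable source of cues to allocation for the person who scores the primary outcome, even while the codes stay sealed.

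The size is unknown. The range of 0.05 to 0.20 SD, with two-sided type I error of about 0.055 to 0.13, rests on an assumed guess rate of 65 to 80%, a shift of 3 to 4 points in favour of the extract and an SD of 12 to 18. It should not be read as the effect of the meeting or as evidence that bias will occur. The conclusion also assumes that raters are among the research staff who meet, which is the natural reading but is not spelled out.

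This is a cheap improvement to the protection of the primary outcome. Sample size and power are unaffected.

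**What to change.** Amend section 9 to say that staff who rate the PANSS do not attend, or receive minutes of, the participant-level adverse-event, dose-change and clinical-outcome items for participants they rate. They can still attend the recruitment, confidentiality and procedural items. Where existing staffing allows, add that a staff member other than the rater completes the side-effect checklist in section 7.3 for that participant.

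Safety oversight is unchanged, because the P.I. and the remaining staff still review every event, and the PANSS and other ratings can still be passed to them for safety monitoring as section 7.3 intends.

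The cost is a short amendment, a split agenda and some division of participants between existing staff. The documents give no staffing numbers, so each site must judge how far the division is practicable. Where one person both rates and collects side effects, the meeting change closes only part of the route and the gain is partial.
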